2.1 Introduction

COVID-19 is a rapidly emerging pathogen that has recently been declared a pandemic by the World Health Organization (WHO). No targeted therapeutic treatments for coronavirus (COVID-19) have been identified. Symptoms range from mild upper respiratory tract infection to profound hypoxia, severe pneumonia, ARDS and death. Progression of end stage disease is unpredictable with high fatality rates in mechanically ventilated patients as a result of multi-organ failure. Among patients who require hospitalization, mortality may be 5% to 15%, and for those who become critically ill, reported mortality ranges from 22% to 62%.

Prostacyclin therapy—available in oral, inhaled, and intravenous forms—is an analogue which mimics endogenous prostacyclin (PGI2). Prostacyclin binds to its receptor (a G-protein coupled receptor) found on the surface of vascular smooth muscle and platelets, activates cyclic adenosine monophosphate (cAMP), and results in inhibition of platelet aggregation, vascular smooth muscle relaxation and vasodilation of the pulmonary arteries (Mitchell, Ali et al. 2008). Prostacyclins are most commonly used in the treatment of PAH due to their potent vasodilatory effects. In addition, prostacyclin analogs also inhibit platelet aggregation and may reduce prothrombotic effects of endothelin.

The rationale for use of vasodilators in COVID-19 patients rests on their rapid local effect on the pulmonary vasculature, which has shown to lead to increased oxygenation in other diseases, such as PAH (Higenbottam, Wheeldon et al. 1984) and post-surgical PH (De Wet, Affleck et al. 2004). Epoprostenol has the additional advantage over inhaled nitric oxide in that it may be directly administered through a standard ventilator (closed-circuit).

The rationale for aerosolized prostacyclin use in COVID-19 patients experiencing hypoxia leading to cardiac failure is two-fold:

- (1) inhaled prostacyclin therapy has been used in the treatment of ARDS and has been shown to improve oxygenation and ventilation-perfusion mismatch (see Section 9). Prostacyclins, such as epoprostenol, promote pulmonary vasodilation via a cyclic adenosine monophosphate-mediated decrease in intracellular calcium (Figure 4). While it has not been associated with improved outcomes, such as mortality, and it's use in ARDS is off-label, it may be used in severe life-threatening hypoxemia refractory to conventional ARDS management, such as has been seen in COVID-19.

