6. CRITERIA FOR EVALUATION

6.1 Primary Endpoint

- 1. Reduction of respiratory failure. Failure is defined by any one of the following:
 - Requires VV ECMO
 - Inability to extubate within 10 days or reintubation within < 24 hours
 - Change in S/F, oxygenation index and P/F ratio (≥15%) from baseline to 12 hours, Days 1, 2, 3, 4, 5, 6, 7, 8, 9 and Day 10 (or end of treatment)

or

- 2. Reduction of cardiac or circulatory failure. Failure is defined by any one of the following:
 - Need to begin inotropic therapy or 10% increase in current vasopressor therapy
 - Worsening hemodynamic parameters
 - Cardiac troponin >20% from baseline
 - BNP > 15% of baseline
 - Need for temporary mechanical circulatory support (IABP, Impella)
 - Requires VA ECMO

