6.2 Secondary Endpoints

- 1. Improvement in oxygenation defined as any one of the following:
 - Stabilization of PaO2/FIO2 >250
 - Improvement in FIO2 by 50% or improvements ≥15% in S/F, P/F ratio from baseline at 12 hours, Day 5 and Day 10 (or end of treatment)
- 2. Improved clinical outcomes defined as one of more of the following:
 - Time to extubation following the site's extubation protocol

- Free from re-intubation
- Reduction in ICU days
- Reduction in the number of re-admissions to the ICU due to COVID-19 within 28 days
- Reduction in total hospital days
- Mortality [28 days] defined as Cardiopulmonary mortality from all causes

3. Safety and tolerability

 Monitoring of adverse events (AEs), serious adverse events (SAEs), chest CT or Chest X-rays, vital signs, ventilatory/oxygenation parameters, and laboratory tests.

6.3 Exploratory endpoints will include (where available as part of standard of care):

- Change in LDH
- Change in fibrinogen
- Change in WBC count including lymphocytes and neutrophil subsets
- Change in triglycerides
- Change in ferritin
- Change in CRP / ESR
- Change in IL-6
- Change in D-Dimer

Changes in these parameters will be assessed for each patient from baseline to end of study as well as changes between the active and control groups.

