9.1.2 Days 1-10 Treatment

9.1.2.1 Randomization

- Evaluate that the patient continues to be eligible for the study by assessing Inclusion/Exclusion Criteria.
- Once eligibility has been confirmed, a Subject number beginning with 101 and rising sequentially will be assigned to the next enrolled subject.
- A blinded order for the Investigational Drug Services group will be generated by EPIC for the next sequential subject to be randomized.
- The unblinded pharmacist will prepare the treatment assignment (Active or Control) for the next assigned Subject number.
- The reconstituted study drug will be protected from light and labelled in a blinded manner to ensure maintenance of the study blind.
- Subjects will be randomized to receive either Active or Control for a maximum of 10 days, as clinically indicated and at the discretion of the Investigator.

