9.1.2.4 Days 2-10 (While on study drug)

- Continue to administer study drug if clinically indicated.
- Adverse Event/SAE assessment daily
- Concomitant medication evaluation daily
- Oxygenation measurement via continuous pulse oximetry (SpO₂)
- Ventilatory parameters assessed twice daily: Ventilator Type, Vent Mode, FiO₂, Inspiratory time, Mean Airway Pressure, Peak Inspiratory Pressure, Positive End Expiratory Pressure, Tidal Volume, and Respiratory Rate
- Vital signs will be assessed twice daily in AM and PM. Efforts will be made to obtain vital signs at the same time each day. Vital signs include: temperature, pulse rate, and blood pressure.
- Time Prone Position-16 hours per day per OSU Protocol

- Chest X-ray (Days 3-8 as clinically indicated)
- Full Chemistry Panel including LFTs, CBC with Diff including neutrophils and lymphocytes, PT/PTT, troponin, and BNP(Days 5 & 10).
- Triglycerides, LDH, ferritin, fibrinogen, CRP, ESR, IL 6 and D-Dimer may be collected if the subject's condition warrants it at Days 5 and Day 10.
- Obtain weight. (Day 10 only or at end of study drug dosing)

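### The circulatory limb of the primary endpoint omits death and has no time window, and the sections on collecting troponin, BNP and vital signs disagree about what happens once study drug stops

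*Combined protocol and SAP*

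**What the plan says.** All references are to the current version, the last of the four in the file.

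- **Circulatory limb.** Section 6.1 defines it as "Reduction of cardiac or circulatory failure. Failure is defined by any one of the following". The items are "Need to begin inotropic therapy or 10% increase in current vasopressor therapy", worsening hemodynamics, a troponin rise, a BNP rise, temporary mechanical support, and VA ECMO. The synopsis and Section 10.6.1 carry the same six items. None names death or gives a window.
- **Respiratory limb.** It is joined to the circulatory limb by the word or, and it does have time anchors, for example "Inability to extubate within 10 days or reintubation within < 24 hours".
- **Death.** It appears only as a secondary endpoint in Section 6.2: "Mortality [28 days] defined as Cardiopulmonary mortality from all causes".
- **Missing data.** Section 10.3 uses available data and allows neither estimation nor carrying forward. Section 10.1 says that no SAP will be written.
- **Collection.** Section 9.1.2.4 is headed "Days 2-10 (While on study drug" and lists "troponin, and BNP(Days 5 & 10" there. Section 9.1.2.2 ties twice-daily vital signs to time on drug, whereas Section 7.1.1 sets them for Days 1 to 10 with no such limit. Section 4.4 asks for the Day 10 procedures in patients who leave the study before Day 10. The last treatment column of Table 2 is Day 10 or end of study treatment, and it includes troponin and BNP.
- **Duration.** Section 9.1.2.1 gives study drug "for a maximum of 10 days, as clinically indicated and at the discretion of the Investigator".

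**The concern.** Two gaps meet in one limb.

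The first is classification. The list is closed and death is not on it. A patient who dies on Day 3 with no item recorded satisfies none of the six, so a literal reading gives a non-failure. Someone could instead stretch the undefined hemodynamic item to cover the death, or treat the patient as missing. With no SAP to come, that choice would fall to the sponsor after the data exist.

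The second is ascertainment. If the troponin, BNP and hemodynamic items are looked for mainly while drug is running, follow-up for them depends on a duration that the investigator chooses after randomization and that treatment can influence. Patients who stop early, whether through quick recovery or removal for harm, could be looked at less often.

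At stake is whether the circulatory comparison describes the same period in every patient, and whether early deaths count against the arm in which they occur.

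**Working it through.** The plan gives no sample-size calculation or expected failure rate, so there is no figure of its own to reproduce. The check has three parts.

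**1. What each type of patient would have on file**

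| Patient | Troponin/BNP after screening | Vital signs |
|---|---|---|
| Dosed to Day 10 | Day 5 and Day 10 | Twice daily to Day 10 |
| Stops drug on Day 3, stays in the study | One end-of-treatment draw (Table 2); none clearly required afterwards | To Day 3 under Section 9.1.2.2; to Day 10 under Section 7.1.1 |
| Leaves the study on Day 3 | Day 10 set required (Section 4.4) | Not clear after leaving |
| Dies on Day 3 | None scheduled before death | To Day 3 |

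Three items can still be ascertained after a stop: inotrope or vasopressor use, mechanical support and VA ECMO. Section 5.6 records medications and therapies during the study, Section 7.2.1 records adverse events to Day 28, and Section 9.1.3 reviews concomitant medications at Day 28.

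**2. How many early deaths to expect**

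Inputs: 10 patients per arm (Section 3.3) and 22% to 62% mortality in the critically ill (Section 2.1). The share of deaths falling by Day 10 is not in the documents; 25% to 75% is assumed.

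- Expected early deaths per arm = 10 × mortality × share.
  - At 22%: 10 × 0.22 × 0.25 = 0.55, up to 10 × 0.22 × 0.75 = 1.65.
  - At 62%: 10 × 0.62 × 0.25 = 1.55, up to 10 × 0.62 × 0.75 = 4.65.
- Chance of at least one early death among 20 = 1 − (1 − mortality × share)^20.
  - At 22%: 68% to 97%.
  - At 62%: 97% to nearly 100%.

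These are all early deaths, not only those with no item recorded. One reclassified patient moves an arm's rate by 1/10 = 10 points.

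**3. What classification does to the comparison**

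Let d be the proportion dead by Day 10, q the circulatory failure rate in the others, and u the share of early deaths with no item recorded.

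- Rate as written = (1 − d)q + d(1 − u).
- Rate with death as failure = (1 − d)q + d.

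Take q = 40% (assumed), d = 11% on Active and d = 31% on Control. The two values of d are half of 22% and half of 62%, set apart for illustration only.

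| | Active | Control | Active minus Control |
|---|---|---|---|
| As written, u = 0.25 | 43.9% | 50.8% | −7 points |
| As written, u = 0.5 | 41.1% | 43.1% | −2 points |
| As written, u = 1 | 35.6% | 27.6% | +8 points |
| Death as failure | 46.6% | 58.6% | −12 points |

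As written, the difference equals (d Active − d Control) × (1 − u − q). It reverses sign once u exceeds 1 − q, here 60%. With equal early mortality in both arms (and the same q and u) the difference stays at zero, although each arm's rate falls.

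For scale, the 95% CI half-width for a difference at rates near 50% is 1.96 × √(2 × 0.25/10) = 0.44, or about 44 points.

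**The case against.** **The limbs are joined by or, and every patient enters ventilated.** A death before extubation fits the respiratory item on inability to extubate, so the combined endpoint may already count it. This largely stands for deaths on the ventilator, though the plan does not say so. It does not cover a patient extubated before Day 10 who then dies without reintubation. Nor does it help if the circulatory limb is shown alone, which is possible because the limbs are numbered separately and the synopsis plans to summarize success or failure on any of the endpoints.

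**A reader might infer that troponin, BNP and hemodynamics are collected only while on drug.** The documents do not support that. Section 7.1.1 sets vital signs for Days 1 to 10, Table 2 gives an end-of-treatment draw, and Section 4.4 requires the Day 10 set in those who leave the study. Adverse events and concomitant medications sit under the same on-drug heading in Section 9.1.2.4, yet both are followed to Day 28. What stands is a conflict between sections.

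**A reader might infer that drug duration alone could separate two arms of equal risk by about 10 points.** With a failure hazard of 0.05 per day and exponential time on drug capped at Day 10, the proportion failing on drug is λ/(λ + μ) × (1 − e^(−10(λ + μ))). That is 18% at a mean of 5 days and 28% at 12 days. The arithmetic is right, but it assumes that no circulatory failure of any kind is seen after drug stops, and three of the six items can be. The hazard and durations are not from the documents either.

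**A reader might also infer that more early deaths on Active would lower its failure count.** That holds only if the share of early deaths with an item recorded is below the failure rate in the other patients. Section 2.1 attributes deaths in ventilated patients to multi-organ failure, so many may have had an item recorded first. In addition, a patient removed under Section 4.4.1 for a vasopressor increase above 25% already meets the 10% item.

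**Counting any-cause death as failure is one choice among several,** and it puts non-circulatory deaths into a circulatory measure. That is fair, and it is why deaths should also be shown separately.

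**Conclusion.** The point holds in a limited form. The circulatory limb is a closed list without death and without a window, and nothing in the plan classifies a patient who dies or stops drug before Day 10. An early death with no item recorded scores as a circulatory non-failure on a literal reading. Ascertainment of the troponin, BNP and hemodynamic items depends on drug duration to the extent that the on-drug sections are followed, because no repeat draw is clearly required between drug stop and Day 10.

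Each reclassified patient is worth 10 points in an arm of 10, and at least one early death in the trial is likely under the assumed timing. The direction of any bias cannot be stated in advance. The −7 to +8 point range in the illustration rests on assumed values of d, q and u. All of it lies within the roughly 44-point half-width, so this should be corrected but does not by itself undo an exploratory trial. It still matters because the point estimate is what such a trial passes on.

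**What to change.** 1. In Section 6.1, Section 10.6.1 and the synopsis, assess every circulatory item over one fixed window, from first dose to the end of Day 10, whether or not the patient is still on study drug.
2. In the same places, count death from any cause by Day 10 as failure in the primary endpoint, including when the circulatory limb is reported alone. Show deaths separately as well.
3. Reconcile Sections 4.4, 7.1.1, 9.1.2.2 and 9.1.2.4 and Table 2 so that vital signs and the Day 5 and Day 10 troponin and BNP are collected by calendar day for every patient still in hospital.

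The cost is endpoint and schedule wording, plus at most two routine blood draws in patients who stop drug early. Vital status and medication records are already collected. The downside is slightly higher failure rates that include some non-circulatory deaths and some events off drug.

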Exclusion Criteria	Patients are NOT eligible for this study if they meet any of the following criteria: 1. Patients on ECMO support. 2. Patients receiving another inhalation research medication or inhaled nitric oxide. 3. Not expected to survive for 48 hours. 4. Pregnant (positive pregnancy test in a pre-dose examination) or breastfeeding 5. Open tracheostomy. 6. Clinical contra-indication, as deemed by the attending physician. 7. Allergy to Epoprostenol and its diluent 8. Using inhaled vasodilators at baseline. 9. Patients who are hemodynamically unstable as determined by investigator 10. Patients with significant hemoptysis as determined by investigator
Study Treatment(s)	Patients will receive study drug via mechanical ventilator, starting at 13.6 ng/kg/min. If determined by the treating physician, study drug can be up titrated in 3.4 ng/kg/min increments to a maximum of 30.6 ng/kg/min or down to a minimum of 3.4 ng/kg/min. At the Investigator's discretion, the patient will be weaned off the drug in 6.8 ng/kg/min increments. Study drug will be administered based on the pump rate calculated for active treatment in mL/hr. Study drug can be administered up to 10 days.
Duration of Treatment	The duration of study participation for each patient is as follows: • Screening: up to 14 days • Treatment: up to 10 days • Follow up: 28 days
Criteria for Evaluation	Primary Endpoint 1. Reduction of respiratory failure. Failure is defined by any one of the following: • Requires VV ECMO • Inability to extubate patient within 10 days or reintubation within < 24 hours • Change in S/F, oxygenation index and P/F ratio (≥15%) from baseline to 12 hours, Days 1, 2, 3, 4, 5, 6, 7, 8, 9 and Day 10 (or end of treatment) or
	 Reduction of cardiac or circulatory failure. Failure is defined by any one of the following: Need to begin inotropic therapy or 10% increase in current vasopressor therapy Worsening hemodynamic parameters Cardiac troponin > 20% from baseline BNP ≥ 15% of baseline Need for temporary mechanical circulatory support (IABP, Impella) Requires VA ECMO
	Secondary Endpoints: 1. Improvement in oxygenation defined as any one of the following: • Stabilization of PaO2/FIO2 >250 • Improvement in FIO2 by 50% or improvements ≥15% in S/F, P/F ratio from baseline at 12 hours, Day 5 and Day 10 (or end of treatment)

- 2. Improved clinical outcomes defined as one of more of the following:
 - Shorter time to extubation following the site's extubation protocol

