Chemistry (including AST, ALT, AP, T. Bili) CBC, PT/PTT	X						X					X	
Pregnancy Test (Serum or Urine)	X												
COVID-19 diagnostic test such as molecular or antigen test	X												
Cardiac Troponin, and BNP	X						X					X	
Other blood tests: fibrinogen, ferritin, LDH, Triglycerides, D-Dimer, IL-6, ESR,CRP ⁴	X						X					X	
Administer VentaProst		X	X	X	X	X	X	X	X	X	X	X	
Vital Signs ⁵	X	X	X	X	X	X	X	X	X	X	X	X	
Oxygenation Measurements ⁶		X	X	X	X	X	X	X	X	X	X	X	
Ventilator Parameters ⁷		X	X	X	X	X	X	X	X	X	X	X	
AE/SAE Monitoring		X	X	X	X	X	X	X	X	X	X	X	X
Concomitant Medications		X	X	X	X	X	X	X	X	X	X	X	X
Prone position ⁸		X	X	X	X	X	X	X	X	X	X	X	

- ¹ Informed consent may be obtained after screening study procedures that were conducted as a part of the patient's standard of care.
- ² Height only performed at screening
- ³ Chest CT or CXR may be performed anywhere from 3-8 days as clinically warranted.
- ⁴ These tests are collected only if available as Standard of Care
- ⁵ Vital signs: Prior to initiating VentaProst, Days 1-10 twice daily (morning and evening) at the same time to reduce exposure to Health Care Professionals to include; temperature, pulse rate, blood pressure.
- ⁶Continuous SpO2 via pulse oximetry
- Ventilator Parameters will be collected twice daily along with vital signs and include: Ventilator Type, Ventilator Mode, FiO₂, Inspiratory Time, Mean Airway Pressure, Peak Inspiratory Pressure, Positive End Expiratory Pressure, Tidal Volume and Respiratory Rate
- ⁸Time Prone Position 16 hours per day per OSU protocol

TABLE OF CONTENTS

INV	ESTIG.	ATOR'S SIGNATURE PAGE	3
1.	CLIN	IICAL PROTOCOL SYNOPSIS	4
TAE	BLE O	F CONTENTS	11
		ACRONYMS, ABBREVIATIONS AND	
		ION OF TERMS	14
2.	BACI	KGROUND AND RATIONALE	17
	2.1	Introduction	
	2.2	VentaProst	

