3.4 Duration of Participation

Patients who meet entry criteria will be entered into the study and the duration of study participation for each patient is listed below. The duration of study participation for each patient is as follows:

• Screening: up to 14 days

• Treatment: up to 10 days

• Follow up: 28 days

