7.1.3 Laboratory Measurements

Clinical laboratory measurements to b	e performed are listed below. The Schedule of Assessments			
and Procedures shows the time points a	t which blood will be collected for clinical laboratory tests and			
pregnancy testing. The Baseline for laboratory tests is the Screening assessment.				
Category	Parameters			
	H 11: 1 / PDC WDC '4 1'CC / 1			

Category	Parameters	
Hematology-CBC with diff	Hemoglobin, hematocrit, RBC, WBC with differential (neutrophils, lymphocytes, monocytes, eosinophils, basophils), platelets	
Full Chemistry Panel		
Electrolytes	Sodium, potassium, chloride, bicarbonate, calcium	
Liver function tests	AST, ALT, AP, total bilirubin	
Renal function parameters	BUN, creatinine	
Coagulation Studies	PT/PTT	
Other	Serum or urine pregnancy test, COVID-19 diagnostic test, Troponin, and BNP (fibrinogen, ferritin, LDH, Triglycerides, D-Dimer, IL-6, ESR,CRP may be obtained if the patient's standard of care warrants the tests)	

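### Read as rises, the troponin and BNP failure items have no absolute floor, reference limit or repeat, so small fluctuations can score circulatory failure and dilute the comparison

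*Combined protocol and SAP*

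**What the plan says.** All references are to the last of the four protocol versions in the combined file.

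For the circulatory part of the primary endpoint, Section 6.1 states "Failure is defined by any one of the following". Two of the six items are biomarkers: "Cardiac troponin >20% from baseline" and "BNP > 15% of baseline". The synopsis repeats them as "Cardiac troponin > 20% from baseline" and "BNP ≥ 15% of baseline". Section 10.6.1 carries the same items and also uses ≥ for BNP. The other items include VA ECMO and temporary mechanical circulatory support.

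Section 7.1.3 fixes the comparator: "The Baseline for laboratory tests is the Screening assessment". Section 3.4 allows "Screening: up to 14 days". The Table 2 row "Cardiac Troponin, and BNP" and Section 9.1.2.4 place the later readings at Days 5 and 10.

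No section gives an assay, a CV, a decision limit, a minimum absolute change or a repeat rule for these items. Section 6.4 says only, in general terms, that the measurements are regarded as reliable. Section 10.1 says that no SAP will be written.

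**The concern.** The rule looks only at a ratio of two single readings. As an illustration with invented values, troponin going from 5 to 6.1 (6.1/5 = 1.22) or BNP from 20 to 24 (24/20 = 1.20) is a circulatory failure, whatever the unit and whether or not either value is abnormal. It then counts the same as VA ECMO.

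Each patient can have four comparisons (two markers, two days), and one crossing is enough. If reading-to-reading variation is not small beside 15% to 20%, a noticeable share of patients whose hearts have not changed will be scored as failures. That share is expected to be the same in both arms, so it raises both failure rates and narrows the gap between them. With 10 patients per arm there is little room for that loss.

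The plan is stricter with laboratory values elsewhere. Section 7.2.6 asks for abnormal tests to be repeated before they are reported as adverse events, and Section 10.8.2 looks for markedly abnormal values. The primary endpoint requires neither.

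This point is separate from the missing direction and the loose BNP wording. It remains after both items are rewritten as rises.

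**Working it through.** The plan states no misclassification rate, power or CV, so there is no figure to reproduce.

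**Inputs from the protocol.** Troponin ratio above 1.20; BNP ratio of at least 1.15 (the > or ≥ difference does not matter for a continuous value); one shared Screening baseline; readings at Days 5 and 10; any one item suffices; 1:1 allocation of about 20 patients.

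**Assumptions.** Per-reading CV c, analytical plus within-patient, the same for both markers; lognormal errors, independent between readings and between markers; all readings present; no true change.

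**One later reading.** With σ = √ln(1 + c²), P(false crossing) = 1 − Φ(ln(threshold ratio) / (√2·σ)). At c = 10%, σ = 0.0998 and √2·σ = 0.1411.
- Troponin: 0.1823/0.1411 = 1.292, giving 9.8%.
- BNP: 0.1398/0.1411 = 0.991, giving 16.1%.
- Either: 1 − (1 − 0.098)(1 − 0.161) = 24.3%.

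**Two later readings against the shared baseline.** Simulation of 1,000,000 unchanged patients:

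| CV per reading | Troponin, Day 5 or 10 | BNP, Day 5 or 10 | Either marker, two readings | Either marker, one reading |
|---|---|---|---|---|
| 5% | 0.9% | 4.4% | 5.3% | 2.9% |
| 7% | 5.8% | 13.4% | 18.5% | 10.9% |
| 10% | 16.5% | 25.8% | 38.1% | 24.3% |
| 15% | 30.5% | 38.4% | 57.2% | 39.8% |
| 20% | 39.0% | 45.4% | 66.7% | 48.7% |

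If the CVs differ, for example 10% for troponin and 30% for BNP, the two-reading share is 60%.

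**Break-even.** A threshold equals the one-sided 5% noise limit of a two-reading comparison when ln(ratio) = 1.645·√2·σ. That gives a CV of just under 8% for troponin and 6.0% for BNP.

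**Dilution.** If a share q of patients who would not otherwise fail are scored as failures by noise in each arm, a true rate π is observed as 1 − (1 − π)(1 − q). A true difference is therefore multiplied by (1 − q). Assume, for illustration only, true circulatory failure rates of 60% and 20%. The 40-point difference becomes:
- CV 5%: 40 × 0.947 = 37.9 points
- CV 10%: 40 × 0.619 = 24.8 points
- CV 15%: 40 × 0.428 = 17.1 points
- CV 20%: 40 × 0.333 = 13.3 points

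With 10 per arm, normal-approximation power (crude at this size) is 44% at q = 0. It is 24% at q = 30% (72% v 44% observed) and 16% at q = 50% (80% v 60% observed).

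**The case against.** The strongest objection is that a reader might infer that 20% and 15% lie inside ordinary variation for these markers. The documents do not support that. They give no assay or CV, and at a CV of 5% the noise share is only about 5%. This stands, and the size must be stated as conditional.

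A reader might also infer that one biomarker crossing makes the patient a primary failure. Section 6.1 joins the respiratory and circulatory parts with *or* and never says how they combine. Only circulatory failure is supported.

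The two-reading figures sit towards the upper end for a given CV. Section 9.1.2.4 ties the laboratory draws to time on study drug, and Section 10.3 does not fill in missing values, so some patients will have fewer readings. Positively correlated markers also lower the either-marker share. Some patients with a noise crossing will already have met another item, so the net addition to failures is smaller. All of this reduces the size; none of it supplies a floor or a repeat.

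A reference-limit condition does not remove the noise quantified above in patients already over the limit. That is correct, and how many patients it would help cannot be computed because the documents give no baseline distribution. Choosing it over a repeat rule is a judgement. Requiring the same marker to exceed its threshold on both days would, for instance, cut the 38% at a CV of 10% to about 9%.

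Finally, the trial is exploratory with no formal sample size, and patient listings would let biomarker-only failures be found afterwards. That softens the point, but no composite without the biomarkers is planned.

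**Conclusion.** The concern holds in a limited form. Without any assumption, the documents show two purely relative items with no floor, reference limit or confirming reading. They are measured against a single Screening value, read twice afterwards, and either alone is enough to score circulatory failure.

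The size depends on a CV that the documents do not give. Under the stated assumptions, about 5% to 67% of unchanged patients meet an item by noise for CVs of 5% to 20%; with one post-baseline reading the range is about 3% to 49%. Roughly four in ten or more are affected only if the per-reading CV is about 10% or more.

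The expected effect is dilution of a real difference, not a bias in favour of either arm. This is a cheap improvement to endpoint scoring, not a reason to doubt the design as a whole.

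**What to change.** 1. In Section 10.6.1, pre-specify that the circulatory composite is reported twice, with and without the troponin and BNP items. The second version is free of biomarker noise.
2. In Section 6.1, the synopsis and Section 10.6.1, count a biomarker item only when the post-baseline value has risen by the stated percentage and also exceeds the reporting laboratory's upper reference limit. Use the same inequality for BNP in all three places. This removes trivial rises within the normal range, but not noise in patients already above the limit, which is why the first change is needed as well.

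The cost is one extra summary and one clause per item. The data are already collected and the reference limit is on the laboratory report, so no new procedure is needed. The downside is that a rise that stays within the normal range no longer counts as failure.
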